**Confidential**

---

**Ideal Body Mass of Normal Adults – WOMEN**

| Actual Height              |                                      | Standard Weight in Clothing                 |   |
|-----------------------------------|--------------------------------------|--|---|
| Inches with one inch heels | Centimeters with 2.5 cm heels | Pounds in indoor clothing weighing 5 pounds | Kilograms in indoor clothing weighing 2.3 kg |
| 58.0                              | 147.3                                | 115.0  | 52.2  |
| 58.5                              | 148.6                                | 116.0  | 52.6  |
| 59.0                              | 149.9                                | 117.0  | 53.1  |
| 59.5                              | 151.1                                | 118.3  | 53.6  |
| 60.0                              | 152.4                                | 119.5  | 54.2  |
| 60.5                              | 153.7                                | 120.8  | 54.8  |
| 61.0                              | 154.9                                | 122.0  | 55.3  |
| 61.5                              | 156.2                                | 123.5  | 56.0  |
| 62.0                              | 157.5                                | 125.0  | 56.7  |
| 62.5                              | 158.8                                | 126.5  | 57.4  |
| 63.0                              | 160.0                                | 128.0  | 58.0  |
| 63.5                              | 161.3                                | 129.5  | 58.7  |
| 64.0                              | 162.6                                | 131.0  | 59.4  |
| 64.5                              | 163.8                                | 132.5  | 60.1  |
| 65.0                              | 165.1                                | 134.0  | 60.8  |
| 65.5                              | 166.4                                | 135.5  | 61.4  |
| 66.0                              | 167.6                                | 137.0  | 62.1  |
| 66.5                              | 168.9                                | 138.5  | 62.8  |
| 67.0                              | 170.2                                | 140.0  | 63.5  |
| 67.5                              | 171.5                                | 141.5  | 64.2  |
| 68.0                              | 172.7                                | 143.0  | 64.9  |
| 68.5                              | 174.0                                | 144.5  | 65.5  |
| 69.0                              | 175.3                                | 146.0  | 66.2  |
| 69.5                              | 176.5                                | 147.5  | 66.9  |
| 70.0                              | 177.8                                | 149.0  | 67.6  |
| 70.5                              | 179.1                                | 150.5  | 68.3  |
| 71.0                              | 180.3                                | 152.0  | 68.9  |
| 71.5                              | 181.6                                | 153.5  | 69.6  |
| 72.0                              | 182.9                                | 155.0  | 70.3  |

1 TABLE OF ABBREVIATIONS

Abbreviation	Definition
AE	Adverse Event
BID	Two Times a Day
BSFS	Bristol Stool Form Scale
CDAI	Crohn's Disease Activity Index
CDEIS	Crohn's Disease Endoscopic Index of Severity
CMH	Cochran-Mantel-Haenszel
CRF	Case Report Form
CRP	C-Reactive Protein
DNA	Deoxyribonucleic Acid
DSM-5	Diagnostic and Statistical Manual of Mental Disorders, 5th. Edition
DR	Delayed Release
ECG	Electrocardiogram
EOS	End of Study
EOT	End of Treatment
FDA	Food and Drug Administration
GI	Gastrointestinal
HbA1c	Hemoglobin A1c

HIV	Human Immunodeficiency Virus
IBDQ	Inflammatory Bowel Disease Questionnaire
ICF	Informed Consent Form
ICH	International Conference on Harmonization
IEC	Institutional Ethics Committee
IL	Interleukins
IND	Investigational New Drug
ITT	Intent-to-Treat
LLN	Lower Limit of Normal
LOCF	Last Observation Carried Forward
MedDRA	Medical Dictionary for Regulatory Activities
NASH	Non-alcoholic Steatohepatitis
NF- κ B	Nuclear Factor kappa-light-chain-enhancer of activated B Cells
PCR	Polymerase Chain Reaction
PK	Pharmacokinetic(s)
PP	Per Protocol
PSAP	Pharmacokinetics Statistical Analysis Plan
PXR	Pregnane X Receptor
rCRT	Clinical Remission Rate Treatment
rCRP	Clinical Remission Rate Placebo

RNA	Ribonucleic Acid
ROC	Receiver Operating Characteristics
SAE	Serious Adverse Event
SAS	Statistical Analysis System
SES-CD	Simple Endoscopic Score for Crohn's Disease
SD	Standard Deviation
ULN	Upper Limit of Normal
US	United States
WPAI:CD	Work Productivity and Activity Impairment Questionnaire - Crohn's Disease
WHO	World Health Organization

2 INTRODUCTION

The purpose of this statistical analysis plan (SAP) is to provide details of the statistical analyses that have been outlined within the protocols of Rifaximin delayed release studies including *RECD3125* and *RECD3126*. The scope of this plan includes the final analysis. Any changes to the methods described in this SAP will be documented in each clinical study report (CSR).

3 OBJECTIVES

3.1 Primary Objective

- To determine the efficacy of Rifaximin DR 800 mg BID vs. placebo on the induction of clinical remission and endoscopic response following 16 weeks of treatment in subjects presenting with active moderate Crohn's disease.

3.2 Secondary Objective

A key secondary objective is to evaluate clinical and endoscopic remission following an additional 36-week Long Term Treatment Phase of Rifaximin DR 800 mg BID vs. placebo. The secondary objectives of this study are the following:

- Assess the safety of Rifaximin DR following a 16-week induction, and an additional 36-week Long Term Treatment Phase (i.e., up to 52 weeks of treatment for eligible subjects).
- Assess the population pharmacokinetics of Rifaximin DR.
- Characterize the gastrointestinal microbiota from stool samples, and antibiotic resistance from bacteria cultured from stool samples before and after treatment with Rifaximin DR.
- Evaluate the effects of Rifaximin DR treatment on indices of health outcomes.
- Assess the effects of Rifaximin DR treatment on biological (inflammatory) markers of disease.

This applies to both *RECD3125* and *RECD3126*.

4 ENDPOINTS

4.1 Primary Efficacy Endpoint

There will be two co-primary measures of efficacy for Induction of Clinical Remission and Endoscopic Response:

- Clinical symptom remission defined by (1) the total number of liquid/very soft stools for the 7 days prior to the Week 16 visit being ≤ 10 (from CDAI Item 1); AND (2) an abdominal pain rating of ≤ 1 (from CDAI Item 2) on each day for the 7 days prior to the Week 16 visit.
- Endoscopic response defined as a ≥ 3 -point decrease in the SES-CD from baseline to the SES-CD score obtained between Week 16 and Week 17. SES-CD scores will be calculated from centrally-read digital video of ileocolonoscopies performed at baseline and between Week 16 and Week 17.

For the daily stool data, the number of daily liquid/very soft stools with a consistency of a Bristol Stool Form Scale [BSFS] score of Type 6 or Type 7 will be assessed using the information recorded by the subject via an electronic diary system. The number of liquid/very soft stools in a given week will be calculated as follows:

$$(\text{Number of liquid/very soft stools during that week} \div \text{Number of days with non-missing assessments during that week}) \times 7$$

4.2 Key Secondary Endpoints

The key secondary endpoint is clinical and endoscopic remission. Two key co-secondary endpoints of efficacy will assess this endpoint during the Long-Term Treatment Phase.

- Clinical symptom remission defined by (1) the total number of liquid/very soft stools for the 7 days prior to the Week 52 visit being ≤ 10 (from CDAI Item 1); AND (2) an abdominal pain rating of ≤ 1 (from CDAI Item 2) on each day for the 7 days prior to the Week 52 visit.
- Endoscopic remission defined as a SES-CD score of ≤ 2 at Week 52. SES-CD scores will be calculated from centrally-read digital video of ileocolonoscopies performed at Week 52.

4.3 Secondary Efficacy Endpoints

- Induction of clinical remission defined as a CDAI Score of less than 150 points at Week 16.
- Clinical symptom remission over time: The total number of liquid/very soft stools for the 7 days prior to each clinic visit being ≤ 10 ; AND (2) an abdominal pain rating of ≤ 1 on each day for the last 7 days prior to each clinic visit in $\geq 80\%$ of the study visits during the 52-Week Treatment Period, including Week 52.
- Time until durable response (see Section 7.2) to the liquid/very soft stool component of the co-primary endpoint during the 52-Week Treatment Period.
- Time until durable response (See Section 7.2) to the abdominal pain component of the co-primary endpoint during the 52-Week Treatment Period.
- Proportion of subjects with response to the abdominal pain component of the co-primary endpoint at post-baseline time points.
- Proportion of subjects with response to the liquid/very soft stool component of the co-primary endpoint at post-baseline time points.
- Change from baseline in SES-CD score at Week 16 and Week 52.
- Proportion of subjects with SES-CD score of 0 at Week 52.
- Proportion of subjects who achieve clinical remission by the CDAI endpoint at post-baseline time points.
- Time to loss of CDAI response defined by a CDAI score of 150 points during the Long Term Treatment Phase.
- Percentage of subjects who achieve clinical response at post-baseline time points.
Clinical response is defined as a reduction of at least 100 points from the baseline CDAI score.
- Time to clinical remission based on abdominal pain and liquid stool components of the co-primary endpoints.
- Time to clinical remission based on CDAI < 150 .

- Change from baseline in indices of health outcomes (Inflammatory Bowel Disease Questionnaire [IBDQ], Work Productivity and Activity Impairment Questionnaire for Crohn's Disease [WPAI-CD]) at post-baseline time points.
- Change from baseline in markers of inflammation (e.g. CRP, interleukins, cytokines, fecal calprotectin) at post-baseline time points.

4.4 Safety Endpoints

- Incidence, intensity, and types of adverse events (AEs).
- Changes from baseline in the laboratory parameters (hematology, clinical chemistry, urinalysis).
- Change from baseline in vital sign measurements.

[figure not shown]
5 STUDY OVERVIEW

5.1 Study Design

RECD3125 and RECD3126 are double-blind, placebo-controlled, parallel-group, multicenter, multiregional, 52-week studies to assess the efficacy and safety of Rifaximin DR tablets for the induction of clinical remission and endoscopic response at 16 weeks followed by clinical and endoscopic remission after 52 weeks of continuous therapy in subjects with active moderate Crohn's disease. Subjects with active, moderate disease defined by a CDAI score of ≥ 220 and ≤ 450 points at screening, and evidence of active ileocolonic Crohn's disease defined by a minimum SES-CD of 7 determined during baseline ileocolonoscopy will be eligible for the study. Eligible subjects will complete a 2- to 3-week Screening Period, a 52-week Treatment Period consisting of a 16-week Induction Phase and 36-Week Long Term Treatment Phase, and a 2-week Follow-up Period. Subjects who successfully complete the 2- to 3-week Screening Period and qualify based on CDAI and SES-CD scores will enter the 52-week Treatment Period of the trial and will be randomized in a 1:1 allocation to Rifaximin DR 800 mg BID or placebo. Randomized subjects will have subsequent ileocolonoscopies conducted at the end of the Induction Phase (between Weeks 16 and 17), and following completion of the 36-week Long Term Treatment Phase (Week 52) to assess the effects of treatment on the degree of mucosal healing. Assessments of efficacy and safety will be performed during clinic visits at Weeks 0

(baseline), 2, 4, 8, 12, and 16; then every four weeks through Week 52. All subjects will complete a 2-week (study drug free) Follow-up Period following completion of the 52-week Treatment Period and will return to the clinic for final assessments (End-of-Study [EOS] visit; Week 54). See Figure 1.

Figure 1 Design Schematic

*Baseline ileocolonoscopy can be scheduled at screening visit, or while collecting CDAI data. Performed only after CDAI eligibility confirmed; SES-CD score determined by central endoscopy laboratory

**Ileocolonoscopy performed; SES-CD score determined by central endoscopy laboratory.

***CDAI eligibility based on results of diary data. Hematocrit value, extraintestinal complications, body weight, and abdominal mass are assessed at Visit 1.

6 TREATMENT DESCRIPTION

There are two treatment groups as listed below. All treatments will be administered twice daily at morning and evening. The duration of the treatment is 52 weeks.

- Treatment A: Rifaximin DR Tablets 800 mg BID
- Treatment B: Placebo BID

7 STATISTICAL ANALYSIS METHODS

7.1 General Considerations

All data for enrolled subjects will be presented in data listings by subject number.

Continuous data will be described using descriptive statistics: number of observations (n), mean, standard deviation (STD), median, minimum, and maximum. Frequencies and percentages will be used for summarizing discrete (categorical) data. When categorical data are presented, the percent will be suppressed when the count is zero. The denominator for all percentages, unless otherwise specified, will be the number of subjects in the specified analysis population.

For those summary tables in which baseline and change from baseline measurements will be presented, the baseline is defined subject to each specific analysis.

Safety data will be analyzed using the observed data. Missing values will not be imputed unless otherwise stated.

If additional analyses are required to supplement the planned analyses described in this SAP after database lock, they may be performed and will be identified in the CSR.

Statistical analyses and summaries will be performed using SAS® Version 9.3 or greater or other validated statistical software as required.

7.2 Randomization and Unblinding

Subjects who successfully complete the Screening Period will enter the Treatment Period and will be randomized in a 1:1 allocation to one of two treatment groups for the duration of the study as assigned by the means of centralized electronic randomization system. Randomization will be stratified by study center within a country.

Only in the case of an emergency, when knowledge of the study drug is essential for the clinical management or welfare of the subject, will the investigator be allowed to unblind a subject's treatment assignment. If the investigator breaks the blind for an individual subject, the reason must be recorded on the CRF and the subject will be removed from the study.

7.3 Sample Size

For sample size justification, reference corresponding study protocols.

Originally planned sample sizes per arm for each of the studies are listed below:

Study	Treatment A: Rifaximin DR Tablets 800 mg BID	Treatment B: Placebo BID
RECD3125	330	330
RECD3126	330	330

Both studies will be terminated early therefore the actual sample size may vary.

7.4 Interim Analyses and Data Monitoring

No interim analyses are planned for this study.

7.5 Analysis Population

The Intent to Treat (ITT) population will include all randomized subjects who take at least one dose of study drug.

The analyses of baseline characteristics, efficacy and safety will be performed for the ITT Population.

7.6 Demographics and Study Summary

7.6.1 Subject Disposition

Subject disposition will be summarized by treatment and study phase and will include the number of subjects entered in the study; number and percentage of subjects who completed or prematurely discontinued (classified by reasons for premature discontinuation); the number of subjects entered in the study at each study site; and the number and percentage of subjects who completed or discontinued at each study site.

7.6.2 Demographics and Baseline Disease Characteristics

Demographic and baseline characteristics will be summarized descriptively by treatment group. Baseline will be defined as the last assessments prior to initiating the Treatment Period. The following demographic and baseline disease characteristics will be summarized:

7.6.2.1 Demographics

- Age (years) = (date of informed consent signed – date of birth)/365.25;
- Age group (<65, >=65);
- Sex (male/female);
- Ethnicity (Hispanic or Latino/not Hispanic or Latino);
- Race (American Indian or Alaskan Native, Asian, Black or African-American, Native Hawaiian or Other Pacific Islander, White, and Other); subjects who identify more than one race will be categorized as “Other”;
- Height (cm);
- Weight (kg);
- Body mass index (kg/m²) = (Weight in kg)/ (Height in m)²;
- Region (US/Rest Of World).

7.6.2.2 Baseline Disease Characteristics

Baseline disease characteristics listed below will be summarized descriptively by treatment group and overall using the ITT population.

- Demographic data (outlined above)
- Baseline CDAI and SES-CD scores
- Duration of the disease (years)
- Location of disease
- Previous steroid use (dose, duration)
- Previous surgery for CD
- Smoking history (nonsmoker/exsmoker/smoker)

7.6.3 Protocol Deviations

All protocol deviations will be listed by subject.

7.6.4 Medical History

All current medical condition and/or other significant medical history will be coded using Medical Dictionary for Regulatory Activities (MedDRA) Version 21.0, listed by treatment, reported term, System Organ Class, and Preferred Term in a subject data listing.

7.7 Efficacy Analysis

The phrases 'statistical analysis' or 'analysis' will be used to mean inferential analysis (such as performing tests of significance, reporting p-values and confidence intervals). When no inferential analysis will be performed, the phrases 'descriptive analysis' or 'descriptive statistics' will be used (for instance, producing summary tables of means, standard deviations, percentages of responders). All efficacy analyses will be conducted on ITT population. All efficacy analyses will adjust for country.

7.7.1 Primary Efficacy Analysis

7.7.1.1 Induction Phase

There will be two co-primary measures of efficacy assessed during the Induction Phase. The first co-primary endpoint is:

- Clinical symptom remission defined by (1) the total number of liquid/very soft stools for the 7 days prior to the Week 16 visit being ≤ 10 (from CDAI Item 1); AND (2) an

abdominal pain rating of ≤ 1 (from CDAI Item 2) on each day for the 7 days prior to the Week 16 visit.

The second co-primary endpoint is:

- Endoscopic response defined as a ≥ 3 -point decrease in the SES-CD from baseline to the SES-CD score obtained between Week 16 and Week 17. SES-CD scores will be calculated from centrally-read digital video of ileocolonoscopies performed at baseline and between Week 16 and Week 17.

For each endpoint, the null hypothesis $H_0: \pi_R - \pi_P = 0$ versus the alternative $H_A: \pi_R - \pi_P \neq 0$ is of interest, where π_R is the binomial parameter for induction of remission/response for the Rifaximin DR group, and π_P is the binomial parameter for induction of remission/response for the placebo group. Subjects who require the initiation of rescue medication and/or surgery for CD will be considered treatment failures from the date of the introduction of the rescue medication and/or surgery, regardless of their actual response data. The Cochran-Mantel-Haenszel (CMH) test, stratified by country, will be used to test the hypothesis. Each null hypothesis of no difference will be rejected if the resulting p-value for the respective statistical test is less than 0.05. Significance for the induction claim will only be declared if both null hypotheses are rejected. As such, the overall Type I error rate will be maintained at the 5% level without adjustment for multiple comparisons.

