#### **4.3.2 Prohibited Therapy**

Use of the following medications is prohibited within the inclusion/exclusion specified pre-study time-frames and throughout the study unless otherwise noted:

- Corticosteroids: Parenteral and rectal steroids are prohibited from the screening visit through the end of the study.
- Any oral or intravenous antibiotic. NOTE: A short course of antibiotic to treat acute conditions (e.g., sinusitis, urinary tract infection) is permitted.
- Use of any drug from the rifamycin class at any time during study participation, including rifaximin, rifampin, rifapentine, and rifabutin. Current international trade names of rifaximin include: Alfa Normix, Colidimin, Faxinorm, Flonorm, Lormyx, Normix, Refero, Rifacol, Rifax-Aw, Rifaxan-Aw, Spiraxin, Targaxan, Tixtar, Tixteller, Xifaxan, Xifaxanta, and Zaxine.
- Any biologicals (e.g., TNF $\alpha$  inhibitor, natalizumab, or similar drugs)
- Cyclosporine, tacrolimus, sirolimus, mycophenolate mofetil, or similar drugs
- Rectal administration of 5-ASA or corticosteroid enemas/foams/suppositories.
- Use of tube or enteral feeding, elemental diet, or parenteral alimentation.
- Introduction of any new probiotics or similar supplements during the study.
- The introduction of any new medication for the treatment of Crohn's disease is prohibited, unless the medication is required in the Investigator's opinion as rescue medication. Subjects receiving rescue medication will be considered treatment failures but should remain in the study.

All concomitant medications, including those taken 30 days prior to screening visit, will be documented (drug name, start and stop dates, and indication) in the concomitant medication section of the CRF.

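### A subject who starts a prohibited Crohn's drug that the investigator does not judge to be rescue is not a treatment failure under the analysis rule, and the protocol does not say whether the banned classes can be rescue

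*SAP*

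**What the plan says.** Protocol 4.3.2 opens its list of prohibited therapies with "Use of the following medications is prohibited within the inclusion/exclusion specified pre-study time-frames and throughout the study unless otherwise noted". The list names biologics, cyclosporine and similar drugs, and "Rectal administration of 5-ASA or corticosteroid enemas/foams/suppositories". For steroids it adds that "Parenteral and rectal steroids are prohibited from the screening visit through the end of the study". None of these bullets carries its own exception.

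The last bullet of the list bars new Crohn's medication "unless the medication is required in the Investigator's opinion as rescue medication", and continues: "Subjects receiving rescue medication will be considered treatment failures but should remain in the study".

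The analysis text (protocol 8.6.1; SAP 7.7.1.1 for Week 16 and 7.7.1.2 for Week 52) says: "Subjects who require the initiation of rescue medication and/or surgery for CD will be considered treatment failures". It thus has two treatment-based failure triggers, rescue medication and surgery for Crohn's disease. Each applies from the date it is introduced and overrides the observed response. Neither document lists rescue drugs or gives an objective criterion for rescue. On deviations, SAP 7.6.3 says only that "All protocol deviations will be listed by subject".

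**The concern.** The failure rule is meant to stop a response achieved on another Crohn's treatment from counting as a success of the assigned arm. For drug treatment it does so only where the drug counts as rescue, and the protocol ties that status to the investigator's opinion. A biologic or steroid enema might be started by an outside physician, or be regarded at the site as a breach of the protocol and not as rescue. It could then leave the subject classed as a remitter.

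This touches both co-primary and both key co-secondary endpoints. It also touches the binary secondary endpoints, which SAP 7.7.2.1 analyses by the same methods. If such use differs between arms, the treatment comparison is biased. Even if it does not, the endpoint depends on a judgement that the plan does not define.

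**Working it through.** **Step 1: does any other rule make such a subject a non-responder?**

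- Worst-case handling (protocol 8.7.2, SAP 7.10.1) acts only on fewer than 4 diary days or a missing SES-CD. A subject with complete data is untouched.
- The protocol's per-protocol set (8.3) removes subjects on entry criteria only: Inclusion 3 and 4, Exclusion 1, 2, 13 and 14. SAP 7.5 and 7.7 use the ITT population alone.
- Prohibited medication is not among the discontinuation reasons listed in protocol 4.5, although the investigator may withdraw a subject at any time. Data may well be present.
- Deviations (SAP 7.6.3) and concomitant medications (SAP 7.8.5) are listed. Neither feeds responder status.

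No rule closes the gap, so the subject is scored as observed.

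**Step 2: the plan's own power figure.** Inputs from protocol 8.2: 40% placebo, 55% rifaximin DR, 240 per arm, alpha 0.05. The test is two-sided by the stated alternative. With d the difference, p̄ the mean rate and n per arm:

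power = Φ{ [d√n − 1.96√(2p̄(1−p̄))] / √(p₁(1−p₁) + p₂(1−p₂)) }

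= Φ{ [0.15 × 15.492 − 1.96 × √0.49875] / √0.4875 } = Φ{ (2.324 − 1.384) / 0.698 } = Φ(1.346) = 0.911.

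This agrees with the stated figure of at least 90% for each co-primary endpoint.

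**Step 3: illustration.** The documents give no rate of prohibited Crohn's medication use. Let m be the share of an arm who would have failed but are scored as remitters after such a drug; the observed rate is the planned rate plus m. All values of m are assumptions. At 240 per arm, 1% is 2.4 subjects, 2% is 4.8 and 5% is 12.

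| m placebo | m active | Observed rates | Power, one endpoint |
|---|---|---|---|
| 0 | 0 | 40% vs 55% | 0.911 |
| 2% | 2% | 42% vs 57% | 0.910 |
| 5% | 5% | 45% vs 60% | 0.911 |
| 2% | 1% | 42% vs 56% | 0.868 |
| 5% | 2% | 45% vs 57% | 0.750 |
| 5% | 0 | 45% vs 55% | 0.592 |
| 0 | 2% | 40% vs 57% | 0.963 |

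With no true effect (40% in both arms) and misclassification on active only, the chance of a false finding in favour of active on one endpoint rises from 0.025 to 0.065 at m = 2%, and to 0.197 at m = 5%. A false induction claim would need both co-primary endpoints, so these are not claim-level error rates.

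The damage comes from imbalance between arms, and its sign follows the arm with the excess.

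**The case against.** **The ban is not absolute.** The lead-in to 4.3.2 allows for noted exceptions, and the rescue bullet can be read as one. On that reading, a biologic started for worsening Crohn's disease is rescue and the subject is a failure. This stands as a fair reading, so it would be wrong to infer that the listed classes are banned outright. But the documents do not say that the rescue bullet overrides the specific bullets. Even if it does, failure still turns on the investigator's opinion that the drug was required as rescue.

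**No rescue flag is described.** A reader might infer that failure hangs on a tick-box or site label. Neither document mentions one. The analysis rule does not say that the drug must be recorded as rescue, and drug name, dates and indication are collected for every concomitant medication. A programmer could therefore derive rescue use from those records. This also stands, but the programmer would be choosing a definition that the SAP does not give, and two programmers could choose differently.

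**Unjudged use may be rare.** Investigators have an open rescue route that keeps the subject in the study, so there is little reason to start a Crohn's drug outside it. This is plausible, and nothing in the documents supports large rates. It limits the likely size but does not remove the gap in the rule.

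**Conclusion.** The point holds as a gap in the failure definition. For a drug, the only trigger is rescue medication, which rests on investigator opinion. A prohibited Crohn's drug not judged to be rescue leaves the subject scored on observed data at Week 16 and Week 52. Whether the banned classes can be rescue is unresolved in protocol 4.3.2.

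The size is unknown. Two stronger conclusions are tempting and are not supported. The first is that the error must favour placebo. Heavier use on placebo is reasonable to expect if the drug works, but the documents do not establish it; balanced use changes power very little, and an excess on active inflates the effect. The second is that the trial loses a stated amount of power. The figures above rest on assumed shares, on users who would otherwise have failed, and on the Week 16 planning rates at 240 per arm. SAP 7.3 says both studies end early and the actual sample size may vary, so those figures are illustrative only. The scoring gap exists whatever the final numbers.

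**What to change.** In SAP 7.7.1.1 and 7.7.1.2, keep rescue medication and surgery as triggers and add a third: first post-randomization use, for Crohn's disease, of any medication prohibited by protocol 4.3.2, whether or not the investigator judged it to be rescue. The subject counts as a failure from that date, as for the existing triggers.

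Identify such use from the coded concomitant-medication records (drug, dates, indication) in a blinded review before database lock. Write down in advance how records with a missing or ambiguous indication are handled. State that medications the protocol permits do not count, for example antidiarrheals under 4.3.1 and short antibiotic courses for acute conditions other than Crohn's disease. Without that carve-out, a first dose of loperamide could be scored as a failure.

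Separately, the sponsor should reconcile the specific bans in protocol 4.3.2 with its rescue bullet. Which drugs may serve as rescue is a clinical decision and is not proposed here.

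The cost is a wording change and a small review of data already collected. Response rates may be slightly lower in both arms.
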